12. Disease Evaluations: To be performed at screening (28-day window allowed) and every 6 weeks from dosing date [Cycle 1, Day 1] (-7/+10 days window allowed for first on-study assessment, ± 10 days window for all other assessments) until Week 49 (~1 year) and then every 12 weeks. All on-study disease assessments should be based on a calendar schedule beginning from the first day of dosing. In general, assessments at screening/baseline as well as on-study are to include Computed Tomography (CT) scan with contrast or Magnetic Resonance Imaging (MRI) of the chest abdomen and pelvis. In addition, at screening/baseline, a MRI with and without gadolinium or CT with contrast of the brain, a whole-body bone scan and evaluation of any superficial lesions will be performed. Subsequent disease assessments should also include whole body bone scans and/or MRI of the brain if metastatic disease is identified at screening/baseline by either the **investigator OR the central radiology reviewer**. Bone scans may be performed at one-half the frequency of other radiology evaluations (every 12 weeks) and should be performed during assessment for confirmation of disease response. All scans will be sent to the central radiology reviewer. More detailed guidance on exceptional circumstances is provided in the protocol (Section 7.3).

- 13 Adverse Events: SAEs are to be reported from the time of informed consent for study participation (i.e., excluding prescreening informed consent) until resolution of all SAEs observed on study (SAEs occurring during the screening period are only reported to the safety vendor). Adverse events will be reported from the first day of study treatment until at least 28 days after last dose of study drug, and until resolution or stabilization of acute AEs and/or ongoing SAEs. Post-treatment 28-day follow-up and beyond may be performed by remote contact (e.g., telephone call).
- 14 End of Treatment: Assessments that have been completed in the previous 3 weeks do not need to be repeated (6 or 12 weeks for tumor assessments in accordance with schedule).
- 15 Long Term Follow-up: Survival status and subsequent therapies will be collected by telephone contact every 2 months (± 14 days) from end of treatment visit until death or lost to follow-up.

Table 3: Schedule of PK, Triplicate ECG, and PD Assessments

	Cycle 1, Days 1 and 15 (± 2 days Day 15 only)			Cycle 2, Days 1 or 15 (± 2 days)		

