9 STATISTICS

Detailed methodology for summary and statistical analyses of the data collected in this study will be documented in a Statistical Analysis Plan (SAP), which will be maintained by the Sponsor. The SAP may modify the plans outlined in the protocol; however, any major modifications of the primary endpoint definition and/or its analysis will also be reflected in a protocol amendment.

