9.2 Data Handling

Listings of all patient data will be prepared. Data summaries will be presented in tabular and/or graphical format and summarized descriptively, by the four groups of patients having genetic tumor alterations activating *MET*, where appropriate. If some (or all) of those four groups of patients show similar objective response rate, data summaries (efficacy and safety) will also be presented for those groups combined as supportive analyses. Response rates will be considered similar between groups, if they are within $\pm 10\%$. Further details of planned analyses will be described in the SAP.

For all variables, only the observed data from patients will be used in the statistical analyses; there is no plan to estimate missing data. Patients without a valid clinical response assessment will be assigned a best overall response of not evaluable (NE). Data from patients who are lost to follow-up or have missing observations before reaching an endpoint in any of the time-to-event analyses will be treated as censored with specific rules defined in the SAP.

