9.3 Analysis Populations

9.3.1 Modified Intent-to-Treat Population

The Modified Intent-to-Treat (mITT) population is defined in each arm as all patients who receive treatment at least one dose of MGCD265 on this study.

The primary efficacy analyses of the primary and secondary efficacy endpoints will be performed in the mITT population.

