9.4.3 Progression Free Survival

Progression-free survival (PFS) is defined as the time from date of first study treatment to first PD or death due to any cause in the absence of documented PD. Censoring for the PFS endpoint will be assigned on the date of the last tumor assessment if no assessment of tumor progression is identified by the central radiology review and the patient does not die while on study. For patients in whom two or more sequential assessments are missed, followed by the finding of tumor progression, the PFS endpoint will be censored on the date of the last tumor assessment before the gap. Patients lacking an evaluation of disease after first study treatment will have their PFS time censored on the date of first dose with duration of 1 day. Patients who start a new anti-cancer therapy prior to documented PD will have the endpoint censored at the date of the last tumor assessment prior to the start of the new therapy. The Kaplan-Meier method will be used to obtain the estimate of median progression-free survival time.

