9.9 Evaluation of Enrollment Stopping Rules

Disease response and progression as documented by the investigator in the CRF will be the basis for evaluation of the enrollment stopping rules. The following guidelines will apply to each treatment arm when determining number of events in the numerator and denominator in the stopping rules:

1. The numerator will include patients with objective responses (PR or CR) at any time prior to disease progression as assessed by the investigator and documented in the CRF. Unconfirmed responses will be included until sufficient time has elapsed to allow confirmation of response; if the response is not confirmed, the response will be excluded from the numerator during subsequent reviews.
2. The denominator will include:
 - a. Patients included in the numerator;
 - b. Patients discontinued from treatment;
 - c. Patients at the second or subsequent on-study disease assessment (scheduled after 4 treatment cycles, at Week 13) without PR, CR or PD (i.e., patient has Stable Disease [SD] or Not Evaluable [NE]).
3. The denominator will exclude:
 - a. Patients on treatment that have not yet reached the first on-study disease assessment;
 - b. Patients on treatment with SD or NE at the first on-study disease assessment (scheduled after 2 treatment cycles, at Week 7).

At each evaluation of stopping rules, the contribution of each participant's experience to the numerator or denominator will be updated based on current data. For example, a patient having SD at Week 13 may contribute only to the denominator at one evaluation, but be included also in the numerator at the next evaluation based on new data documenting PR or CR at Week 19.

A degree of discordance is expected between investigator assessments of disease response/progression and central review of disease response/progression. No attempt will be made to retrospectively apply the later emerging central review assessments to the enrollment stopping rules.

The IDMC may elect to apply the Bayesian Predictive Probability Design only to those patients taking the SDD formulation in order to mitigate the potential confounding effects from formulation change. These details are outlined in the IDMC charter.

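### Section 9.4.3 counts death as a PFS event but censors never-scanned patients on the date of first dose without exempting those who have died

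*Combined protocol and SAP*

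**What the plan says.** Section 9.4.3 contains both sides of the conflict. The endpoint definition reads: "defined as the time from date of first study treatment to first PD or death due to any cause in the absence of documented PD". The first censoring sentence uses the date of the last tumor assessment, and applies only when central review finds no progression and the patient has not died on study. A later sentence in the same paragraph reads: "Patients lacking an evaluation of disease after first study treatment will have their PFS time censored on the date of first dose", at a duration of one day. It attaches no condition about death, and nothing says which sentence takes precedence.

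Section 9.2 says that patients lost to follow-up or with "missing observations before reaching an endpoint in any of the time-to-event analyses will be treated as censored with specific rules defined in the SAP". Section 9 adds that "The SAP may modify the plans outlined in the protocol". The supplied text contains no SAP rule for this case.

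**The concern.** A patient who is dosed and dies before the first on-study scan meets the PFS event definition and also the day-1 censoring sentence. Two programmers could follow the paragraph in good faith and classify the same death differently. The exemption for death is present in one censoring sentence and absent from the other, so someone programming the specific sentence as written would censor a known event.

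That censoring is informative, because the patients removed have the worst outcomes. PFS by central review is a named secondary endpoint, each arm has at most 45 patients in the primary analysis, and Section 3 contemplates an accelerated approval application. A PFS curve without the earliest deaths would look better than the arm's experience.

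**Working it through.** The documents give no PFS median, event count or early-death rate, so there is no PFS figure to reproduce. The check sets the sentences against one another and then works out what the literal rule does.

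**1. When the rule bites.** Take first dose as Day 1. Table 2, footnote 12, puts the first on-study scan at 6 weeks: Day 1 + 42 = Day 43. The window is minus 7 to plus 10 days, so Days 36 to 53. Consider two patients:
- *Dies on Day 30, no scan done.* Event definition: event at Day 30. General censoring sentence: does not apply, because the patient died. Day-1 sentence: applies, censored at one day.
- *Scan without progression on Day 43, dies on Day 60.* Event at Day 60. The day-1 sentence does not apply.

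The conflict is therefore confined to deaths with no post-dose evaluation.

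**2. Effect on the curve.** Let N patients be dosed and let k of them die unscanned before any other event or censoring, with f = k/N.
- Deaths counted: the curve falls to (N-k)/N = 1-f, then follows the other N-k patients.
- As written: the k patients leave on day 1 with no drop, and the curve is that of the other N-k patients, starting from 1.
- Ratio, as written over counted: 1/(1-f) = N/(N-k).

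With N = 45 (Section 9.1) and k assumed:
- k = 2: 45/43 = 1.047
- k = 4: 45/41 = 1.098

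A landmark PFS of 50.0% with deaths counted would thus read 50.0 × 45/43 = 52.3%, or 50.0 × 45/41 = 54.9%.

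**3. Effect on the median.** Take the median as the first time the curve is at or below 50%, with no other censoring before it.
- N = 45, k = 1. Counted: the 23rd event of 45, which is the 22nd among the other 44. As written: the 22nd of 44 (22/44 = 0.5). No change.
- N = 45, k = 2. Counted: the 23rd of 45, which is the 21st among the other 43. As written: the 22nd of 43 (21/43 = 0.488, 22/43 = 0.512). The median moves by one event.
- N = 44, k = 1. Counted: the 22nd of 44, which is the 21st among the other 43. As written: the 22nd of 43. The median moves by one event.

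Most progressions are dated at scheduled scans, so neighbouring events often share a date and a shift of one event often changes nothing.

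**4. Simulation.** All inputs except N are assumptions: N = 45; k unscanned deaths uniform on Days 2 to 95; the others exponential with median 165 days; 85% of their events dated at the next 42-day scan and 15% deaths at the actual time (not before Day 43); administrative censoring uniform on Days 365 to 730. Ratio of mean medians, as written over deaths counted:
- k = 1: 1.00
- k = 2: 1.06, with the two medians identical in about 60% of trials
- k = 4: about 1.135

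Assuming 120 or 240 days instead of 165 gives 1.059 to 1.064 for k = 2 and 1.130 to 1.140 for k = 4. The null result for one death is particular to N = 45: with one death the ratio is 1.06 at N = 44 and 1.10 at N = 28.

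**The case against.** The strongest reply is that the paragraph can be read in harmony. The definition and the first censoring sentence already treat death as an event, Section 9.2 speaks of censoring before an endpoint is reached, and a patient who has died has reached one. On that reading the day-1 sentence only supplies a date for patients who are censorable anyway, and the SAP may say so. This stands as a plausible account of intent. It does not remove the point, because the supplied text does not state that reading and the sentence itself is unconditional. It does limit the conclusion to a contradiction, since the documents do not show that these deaths will be censored.

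Some stronger readings are tempting but unsupported:
- *That day-1 censoring breaches the mITT analysis.* Section 9.3.1 says: "The primary efficacy analyses of the primary and secondary efficacy endpoints will be performed in the mITT population". That names who is analysed. A patient censored on day 1 is still in the set.
- *That Section 9.9 sets a contrary standard by keeping discontinued patients in its denominator.* That section governs response counts for enrollment stopping and says nothing about PFS censoring.
- *That PFS is inflated whenever a never-scanned patient dies.* For deaths on Days 180 to 360 the simulated median ratio for k = 2 is 0.946 to 0.998, so no upward direction can be claimed for late deaths.
- *That Section 9.4.3 already implies a cut-off such as Day 95.* Its gap rule is written for patients in whom "two or more sequential assessments are missed, followed by the finding of tumor progression". It does not address death.

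**Conclusion.** The contradiction in Section 9.4.3 is real and should be resolved before PFS is analysed. Followed literally, the day-1 sentence censors known deaths, and for deaths that precede the other events it can only raise the later curve, by 1/(1-f). The size rests on assumed counts: 4.7% in relative terms for 2 of 45 and 9.8% for 4 of 45. A reader might infer that the reported median will be overstated. The documents do not support that: with 2 of 45 the simulated median is unchanged in about 60% of trials and about 6% higher on average. There is no bias if no such deaths occur or if the harmonised reading is programmed.

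The consequence is bounded. PFS is secondary and has no hypothesis test. ORR and the stopping rules do not use this sentence, and Section 9.4.4 counts every death in OS.

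**What to change.** In the day-1 sentence of Section 9.4.3, insert *and who have not died* after the reference to first study treatment. Add that a death before any post-dose evaluation, without intervening new anti-cancer therapy, is a PFS event on the date of death. Patients who start new therapy before dying stay under the existing new-therapy sentence. Their only prior assessment would be the baseline scan, so the SAP should state the censoring date for them.

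Whether to set a cut-off for late deaths in never-scanned patients, such as Day 95 (second scan at Day 85 plus the 10-day window), is an optional convention for the SAP, and the fix does not depend on it.

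The cost is a clause, one added sentence and minor programming. No new data are needed, because Section 7.6 already follows survival until death or loss to follow-up. The downside is a possibly less favourable PFS estimate.

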9.4.4 Overall Survival

Time to death is defined as the time from date of first study treatment to death due to any cause. Censoring for the survival endpoint will be assigned on the date of the last on-study follow-up that the patient is reported to be alive. The Kaplan-Meier method will be used to estimate the median OS and 1-year Survival Rate; the 95% confidence interval of the 1-year survival rate will also be reported.

9.5 Safety Data Presentations and Summaries

9.5.1 Adverse Events

Adverse events will be classified using the medical dictionary for regulatory activities (MedDRA) classification system. Listings will include the verbatim term, preferred term, and system organ class (SOC). The number of patients with AEs and the incidence of AEs by SOC and preferred term will be summarized. AEs will be summarized by maximum intensity and relationship to study therapy. Separate summaries will be provided for AEs, SAEs, treatment-related AEs, treatment-related SAEs, and other significant AEs (e.g., AEs leading to study discontinuation).

9.5.2 Prior and Concomitant Medications

Collected prior and concomitant medications will be coded by WHO medical dictionary; patients who received these medications will be listed and summarized.

9.5.3 Clinical and Laboratory Assessments

Clinical and laboratory assessments include clinical laboratory tests (hematology, coagulation, and chemistry), vital signs, and 12-lead ECGs.

Clinical laboratory results will be listed by patient and, as appropriate, summarized descriptively, which will include a display of change from baseline. Selected parameters will be presented in shift tables of baseline against worst grade test result. Laboratory values outside of the normal ranges will be identified. Laboratory values that meet Grade 3 or 4 criteria according to NCI CTCAE v.4.03 will be listed and summarized.

ECG assessments will be evaluated for change of QTc from baseline as an exposure: response analysis. The investigator's interpretation of QTc will be used in the clinical management of patients. The study analysis will use Fridericia's formula applied programmatically to the ECG data collected in CRFs.

Vital signs and ECG measurements will be listed for each patient at each visit. Descriptive statistics of observed values and changes from baseline will be summarized by treatment group.

9.5.4 Patient Demographics, Baseline Characteristics and Disposition

Presentations of patient characteristics will include a summary of the following for all patients enrolling in the study:

- Demographics
- Baseline disease characteristics
- Pre-existing conditions/concurrent illness
- Prior therapies/surgeries

A summary of patient enrollment and disposition will include reasons for study discontinuation.

9.5.5 Analysis of MGCD265 Dosing

MGCD265 administration will be described in terms of the total number of cycles administered, the median (range) of cycles administered, dose intensity, and reasons for the deviations from planned therapy.

9.6 Other Study Endpoints

9.6.1 Pharmacokinetic/Pharmacodynamic Analysis

The PK exposure and PD data from this study may be used in the development of population PK and PK/PD models for MGCD265. Additional PK parameters may be defined and described in the Pharmacokinetic Analysis Plan. Plasma concentrations will be listed by subject for the PK Population. Summary statistics of MGCD265 concentrations will be reported by Day and Cycle. Only samples with acceptable PK

(as defined in the Pharmacokinetic Analysis Plan) will be included in the summary statistics and a listing of individual data points or subjects excluded from the analysis will be presented.

9.6.2 Gene Alterations in Tumor DNA

Tumor tissue and ctDNA genetic alterations activating *MET* will be presented descriptively, by treatment arm. Moreover, change-from-baseline in ctDNA will be presented by visit and treatment arm to assess change in genetic alteration status in ctDNA with MGCD265 treatment over time.

A concordance analysis will be conducted between target gene alterations identified in tumor tissue versus ctDNA in individual patients at prescreening/baseline. Cohen's Kappa, sensitivity and specificity will be estimated for ctDNA as well as Spearman's correlations between tumor tissue and ctDNA.

An analysis of covariance will be performed on changes in ctDNA through time including Time and Treatment as fixed effects and ctDNA at baseline as covariate.

Further details of the analyses will be presented in the SAP.

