Long Term Follow-Up ¹⁵								X

Footnotes located on the [following page](#).

1. Study Participation Informed Consent (ICF): May be performed prior to 28 days before first dose of study treatment. Patients entering full clinical screening must have both the pre-screening ICF as well as the clinical screening ICF signed.
2. Tumor Tissue for Genotyping: Collection of tumor tissue may occur well prior to the study screening period (See Table 1). The informed consent process may be performed in accordance with documented institutional practice or using the study-specific, IRB-approved pre-screening ICF. Tumor tissue samples preferred for testing are the most recent tumor sample available; however, testing may be performed on samples taken any time during the disease course. Testing may be performed on primary, recurrent, or metastatic lesions. If study enrollment is based on Sponsor-approved local laboratory results, a tumor tissue sample for retrospective confirmation by the central laboratory is expected to be available and to be collected prior to dosing.
3. Physical Examinations: A complete physical examination required at Screening and End of Treatment only. Height will be recorded at screening only. All other evaluations will be symptom-directed, abbreviated evaluations.
4. Vital Signs: Weight, temperature, blood pressure, respiratory rate, and pulse rate to be assessed prior to dosing as indicated.
5. Pregnancy Test: If the patient is a woman of childbearing potential, negative serum or urine pregnancy test performed by the local laboratory at screening will be required. The informed consent process must include discussion of the risks associated with pregnancy and adequate contraception methods. Additional pregnancy testing may be necessary if required by local practices or regulations, or if potential pregnancy is suspected. For patients enrolled in the United Kingdom, a pregnancy test must be completed within 7 days of Cycle 1 Day 1 (as part of screening or a repeat test). For patients enrolled in Poland, a pregnancy test must be completed within 7 days of Cycle 1 Day 1 (as part of screening or a repeat test), Day 1 (pre-dose) for all subsequent cycles and at the 28-day follow up visit.
6. Indicated Cycle 1, Day 1 Assessments: Repeat assessment on Cycle 1, Day 1 not required if screening assessment performed within 7 days before the first dose.

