1.1.4 Tumor Gene Sequencing Using Blood Plasma

Whereas analytical techniques evaluating tumor genes in tumor tissue have become accepted for identification of patients for clinical trials of targeted therapies, increasing evidence supports the genetic analysis of circulating DNA in the blood plasma of patients with cancer as an effective and quantitative method for evaluating tumor genetic mutation profiles. Tumor cells release a significant amount of DNA into circulation during cancer progression; cell-free circulating tumor DNA (ctDNA) can comprise greater than 90% of total circulating plasma DNA (Bettegowda-2014, Diehl-2008). Correlative analyses have demonstrated a high degree of concordance for detection of selected genetic mutations (e.g., EGFR, KRAS or multi-gene panels with annotated known cancer mutations) between tumor tissue and ctDNA with specificity for plasma vs. tissue concordance of 99% for mutations with allelic fractions > 0.10% (Bettegowda-2014, Newman-2014). The clinical utility of a ctDNA-based assay to identify a patient population that benefits from treatment with a specific therapeutic agent was demonstrated using a plasma DNA-based companion diagnostic to detect EGFR mutations in the tumors of patients with NSCLC treated with gefitinib (Douillard-2014); the result was European regulatory approval for gefitinib in the indication.

Availability of tumor tissue for tumor gene sequencing and other potentially interesting diagnostic testing is inherently limited in the NSCLC disease setting and becoming more problematic with the increasing number of targeted therapies under study and the required testing with multiple co-diagnostic tests. The capability to evaluate tumor mutation status with non-invasive techniques has the potential to benefit a significant segment of the patient population. In addition, specimens available for tumor tissue-based analysis are frequently archival diagnostic biopsy tissue that are not necessarily reflective of tumor genetic status in more advanced and treated disease. A benefit of analysis of ctDNA is that the sample represents a patient's current tumor genetic profile. In addition, it allows ongoing monitoring to identify new mutations that may occur and indicate resistance to treatment.

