7.2 Molecular Testing Methods

Potential study candidates will undergo molecular testing of tumor tissue or blood in order to first establish eligibility of molecular alterations; those patients with qualifying mutations will then undergo clinical screening, and eligible patients [based on both qualifying mutation(s) and clinical screening] will then be assigned into a patient treatment arm upon confirmation of study eligibility.

Testing of tumor tissue is prioritized over ctDNA for the purpose of determining eligibility for this study. Tumor tissue samples preferred for testing are the most recent tumor sample available; however, testing may be performed on samples taken any time during the disease course. Testing may be performed on primary, recurrent, or metastatic lesions. Biopsies having significant risk should not be performed for the purpose of determining patient eligibility, including but not limited to biopsies of the lung/mediastinum or endoscopic procedures extending beyond the esophagus, stomach, or bowel. However, in the event that a patient desires to consider study participation and no tumor specimen is available, procedures having less risk may be considered.

Tumor tissue or ctDNA may be tested using the Sponsor-provided central laboratory or a Sponsor-approved local laboratory to establish eligibility, with follow-up tissue or ctDNA sample(s) retrospectively analyzed in the Sponsor-provided central laboratory.

Qualifying results by ctDNA testing may be the basis for study eligibility if the search to locate tumor tissue that is suitable for testing shows that none exists.

The analytical techniques employed by the Sponsor-provided central laboratories and criteria for acceptable genetic tumor alterations for this study are described in the Study Laboratory Manual. Included are:

1. Gene panels for the next generation sequencing tests for tumor tissue and ctDNA samples,
2. List of *MET* mutations known to be activating,
3. Description and use of RT-PCR for detection of *MET* exon 14 deletion mutations, and
4. Definitions for quantitative thresholds for positive test results.

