7.5.3 Circulating Tumor DNA

Blood samples for ctDNA analysis will be collected at pre-screening or baseline, at the time of disease evaluation to confirm a disease response (PR or CR) and at the End of Treatment visit, as outlined in Table 2. For patients who are enrolled based on prospective ctDNA testing, an additional sample may be requested prior to dosing to ensure adequate amounts of blood have been received to complete the remainder of analyses required per protocol. Parameters that will be evaluated include but are not limited to *MET* mutations, *MET* gene amplification, *MET* gene rearrangement, and other genetic mutations or gene copy number changes associated with the pathogenesis of human cancers.

At each ctDNA time point, blood samples will be collected into two 10mL Streck brand Cell-Free DNA Blood Collection tubes allowing shipping and stability at ambient temperatures. For ctDNA analysis, the total volume of blood to be collected between pre-screening and End of Treatment will be up to approximately 60 mL of blood.

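### ctDNA sensitivity and specificity are scored against tissue of any age, so the planned estimate cannot separate assay disagreement from elapsed time and intervening therapy

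*Combined protocol and SAP*

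**What the plan says.** Section 9.6.2 defines the analysis: "A concordance analysis will be conducted between target gene alterations identified in tumor tissue versus ctDNA in individual patients at prescreening/baseline". Besides Cohen's kappa and Spearman correlations, it says that "sensitivity and specificity will be estimated for ctDNA". Only two tests are compared and ctDNA is the one being scored, so tissue is the reference by implication, although the section does not say so outright.

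On the age of the tissue, section 7.2 prefers the most recent sample but adds that "testing may be performed on samples taken any time during the disease course". Table 1 says the same, and footnote 2 to Table 2 notes: "Collection of tumor tissue may occur well prior to the study screening period". On the blood, section 7.5.3 says: "Blood samples for ctDNA analysis will be collected at pre-screening or baseline".

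Section 1.1.4 compares the two materials. Of tissue it says that "specimens available for tumor tissue-based analysis are frequently archival diagnostic biopsy tissue that are not necessarily reflective of tumor genetic status"; the status it has in mind is that of later disease, after progression or therapy. Of blood it begins "A benefit of analysis of ctDNA is that the sample represents" and goes on to name the patient's current tumor genetic profile.

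Section 9.3.3 admits to the molecular marker population any mITT patient with tissue and/or ctDNA results and sets no condition on timing. Section 9.6.2 has no interval limit, stratum or sensitivity analysis, and leaves further detail to the SAP.

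**The concern.** Sensitivity and specificity assume that the reference shows the state the index test is trying to detect. Here the reference may predate the blood by one or more lines of treatment. If an alteration present in old tissue has gone by the time of the blood draw, a correct negative ctDNA result is scored as a miss. If an alteration has appeared since the tissue was taken, a correct positive is scored as a false positive.

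Such gaps are likely to occur. Inclusion criterion 2 requires at least one prior platinum or immunotherapy regimen for advanced disease. Section 7.2 rules out significant-risk biopsies, including lung and mediastinum, done only to establish eligibility. Diagnostic tissue will therefore often be all there is.

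The agreement between tissue and ctDNA is a stated secondary objective (section 2.1.2), and section 1.1.4 cites concordance with tissue as support for using ctDNA to select patients. If agreement in this trial came out low, the planned analysis could not show whether the assay or the passage of time was responsible.

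**Working it through.** Section 9.6.2 states no expected value, so there is no plan figure to reproduce. The arithmetic below only shows how the effect works.

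**Inputs**
- Se = 0.85 and Sp = 0.98, from the platform evaluation in section 1.1.4. The sensitivity there is given as more than 85%, so 0.85 is a lower bound.
- L = share of tissue-positive patients whose alteration is absent when blood is drawn. Not in the documents; assumed 5%, 10% and 20%.
- G = share of tissue-negative patients who have gained an alteration by the blood draw. Not in the documents; assumed 10% and 20%.
- Assumption: Se and Sp describe performance against status at the time of the blood draw.

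**Sensitivity.** Apparent sensitivity = Se(1 − L) + (1 − Sp)L.
- L = 5%: 0.85 × 0.95 + 0.02 × 0.05 = 0.8085, reported here as 80.8%
- L = 10%: 0.85 × 0.90 + 0.02 × 0.10 = 0.767
- L = 20%: 0.85 × 0.80 + 0.02 × 0.20 = 0.684

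The drop equals L(Se + Sp − 1) = 0.83L, about 4, 8 and 17 percentage points. With Se anywhere from 0.85 to 1, the drop lies between 0.83L and 0.98L.

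**Specificity.** Apparent specificity = 1 − [G × Se + (1 − G)(1 − Sp)].
- G = 10%: 1 − (0.085 + 0.018) = 0.897
- G = 20%: 1 − (0.170 + 0.016) = 0.814

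**Kappa.** At an assumed 50% tissue positivity, chance agreement is 0.5.
- L = G = 0: observed agreement is (0.85 + 0.98)/2 = 0.915, so kappa = (0.915 − 0.5)/0.5 = 0.83
- L = G = 10%: observed agreement is (0.767 + 0.897)/2 = 0.832, so kappa = (0.832 − 0.5)/0.5 = 0.66

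At an assumed 80% positivity the same change takes kappa from 0.68 to 0.51.

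The assay is the same in every row; only the age of the reference differs. Loss alone moves sensitivity, and gain alone moves specificity. Kappa falls in either case, but it is symmetric and does not say which test is wrong.

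**The case against.** The case on the other side has real force.

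- **Detail is deferred.** Section 9.6.2 refers to a SAP, and the document reviewed contains no separate SAP text. A reader might infer that no interval rule exists anywhere. What can be said is that the protocol text contains none. Nor does 9.6.2 say that all pairs will be used; it simply restricts none.
- **The timing gap can be narrow.** The most recent tissue is preferred. Blood can be early too: footnote 10 to Table 2 allows ctDNA collection well before screening, and the text above Table 1 allows pre-screening during the required chemotherapy.
- **MET status may be stable in this population.** Prior MET or HGF inhibitors and known EGFR or ALK positivity are exclusions, and the acquired MET amplification described in section 1.1.3 arises under EGFR inhibitors. Section 3 expects high correlation for mutations. Against this, section 1.1.3 also links MET to resistance to chemotherapeutics, so change cannot be ruled out.
- **The illustration may count timing twice.** The 85% and 98% came from paired tissue and plasma on 10 markers, with sampling intervals not stated. Some timing disagreement may already be in them. A reader might infer that 4 to 17 points of sensitivity are lost to timing in this trial; the documents do not support that or any other value.
- **Agreement with available tissue is useful in itself.** A reader might infer that the estimate measures nothing interpretable. That goes too far: it answers how often the two tests agree in practice, and no decision rule depends on it.

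The central point stands. Tissue of any age is the implied reference, section 1.1.4 says such tissue may be out of date, and nothing in the protocol text separates the pairs by timing.

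**Conclusion.** The concern holds in a limited form. Real change in MET status between samples would lower apparent ctDNA sensitivity or specificity, and would lower kappa without blaming either test. The estimate as outlined cannot separate assay disagreement from elapsed time and intervening therapy.

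The size is unknown. It depends on the mix of sample ages and on the rate of MET change, neither of which is in the documents, and it could be small if most tissue is recent. The figures of 80.8% to 68.4% rest on an assumed 5% to 20% loss and on reading the platform performance as performance against current status.

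The reach is confined to one secondary objective. The primary ORR analysis and the stopping rules do not use this estimate. Entry requires a positive result in tissue or ctDNA, so tissue-negative patients are few and selected. That separately distorts specificity and is not cured by the change below.

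**What to change.** In section 9.6.2, or in the SAP text it points to:

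1. Keep the estimate from all pairs, but label it positive and negative percent agreement of ctDNA with available tissue.
2. Add kappa, sensitivity and specificity by tissue-to-blood interval, with the cut-point fixed before analysis, and by whether systemic therapy was given between the samples. The documents offer no basis for a particular cut-point, so the sponsor should choose and justify one.
3. State that the contemporaneous stratum without intervening therapy is the one used to interpret assay performance, with exact confidence intervals and the number of pairs shown.
4. Confirm that tissue and blood collection dates are captured. Section 7.1.1 asks for the method and result in the CRF but does not mention the sample date. Prior therapy is already collected at screening (Table 2).

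The cost is some added wording and a little more analysis. The contemporaneous stratum may be small, with wide intervals, because every patient is pretreated, tissue is scarce, and Arms C and D are intended for patients without usable tissue. That is the reason to add the strata beside the estimate from all pairs and not to replace it.
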